PROTOCOL: Racial Differences in the Natriuretic Peptide Response to Glucose Challenge

Study Design, Setting, and Location

Our study was a single-center, prospective, physiological clinical trial approved by the institutional review board at the University of Alabama at Birmingham (UAB). Participants were recruited from the university campus and surrounding areas. All participants signed informed consent.

Sample Selection

Prospective participants were first contacted by phone to determine eligibility prior to scheduling a screening visit at the clinical research unit (CRU). Self-identified healthy black and white men and women were eligible to participate in the clinical trial based on the following criteria: between 18 and 40 years of age, blood pressure (BP) less than 140/90, estimated glomerular filtration rate >60 ml/min, and willingness to adhere to the study diet. Exclusion criteria included the following: history of hypertension, history of cardiovascular, renal, or liver disease, history of diabetes or glucose-lowering medications, use of vasoactive or diuretic medications, anemia, abnormal serum sodium or potassium, pregnancy, elevated liver function tests defined as >3x the upper limit of normal, women taking hormonal birth control, history of smoking, body mass index (BMI) <18.5 kg/m², or regular use of non-steroidal anti-inflammatory medications.

Study Protocol

For the screening visit, subjects were educated on the study protocol and directed to complete a questionnaire regarding medical and family history. The study investigators further evaluated subjects who agreed to the study and signed consent. Blood was drawn for a basic metabolic profile, liver enzymes, and complete blood count. Additional samples were collected if consent was provided for DNA extraction and gene expressions for NPs. The CRU nursing staff obtained height, weight, and BP (i.e., an average of three BP measurements) for a baseline. Female participants provided a urine sample to test for pregnancy. Before completion of the screening visit, subjects met with the registered dietitian to discuss the study diet and were provided with a 3-day meal log to assess dietary habits.

Upon review of screening labs, eligible subjects were enrolled in the study [stratified by race using permuted blocks for age and sex] and invited back for food pick up and protocol (i.e., a high-carbohydrate challenge) visits. Within seven days after the screening visit, participants visited the CRU metabolic kitchen for food pick-up. Three days of standardized meals were provided to be consumed for the three days leading up to the protocol visit. Three meals per day and snacks were provided based on participant preferences and by following macronutrient RDAs from the USDA 2005 Guidelines. The study nutritionist calculated caloric needs. In brief, each study participant was provided on an average 1,993 kilocalories worth of meals comprising 4,667 mg of sodium per day for three days. The contribution of carbohydrate, fat, and protein in total caloric intake was 51%, 31%, and 18%, respectively. Additional instructions were given to drink only water, to refrain from alcohol and caffeine use, and to consume only

food provided by CRU metabolic kitchen for the remainder of the study. Participants were also advised to avoid strenuous activities for 24 hours prior to the protocol visit. For the protocol visit, participants fasted overnight for 10 hours, before reporting at 7:00 AM to the CRU. Upon arrival, participants were assessed for compliance with the study diet and were positioned in the sitting position with the back-rest at 45 degrees and legs elevated. Heart rate, oxygen saturation and BP (an average of three measurements using a Carescape V100 monitor) were obtained. Participants were given glucola, a 75mL, 75g glucose equivalent, and were provided only distilled water to drink as needed for the remainder of the protocol. Blood pressure was measured every 30 minutes, and heart rate and oxygen saturation were measured every 60 min. Blood was drawn in 60 min intervals for 8 hours for biomarker profiling. All the participants remained in fasting state (except distilled water) till the end of the study protocol.

Statistical Analyses

Our study was powered to detect the change in ANP levels in response to a high-carbohydrate challenge among black individuals. Based on a prior investigation among Whites, a high-carbohydrate challenge can reduce circulating plasma ANP levels up to 27%. With an estimated standard deviation of 0.2 (a high estimate) and utilizing prespecified sample size of 30 black individuals, our study was powered to detect a change as small as 11% in ANP levels after a high-carbohydrate challenge, with $\beta=0.8$ and $\alpha=0.05$. We expected a similar effect size for change in ANP levels after a high-carbohydrate challenge among whites.

All analyses were conducted using STATA, version 14.2 MP (StataCorp LP), and LIMMA R package. Baseline characteristics of participants were compared between blacks and whites using Student's t-test (normal distribution) or Mann-Whitney test (non-normal distribution) for continuous variables and Pearson χ^2 test for categorical variables. The normality of continuous variables was assessed using histogram and Q-Q plots (visual assessment) as well as Shapiro Wilk test (statistical assessment). Plasma NP levels at baseline and after a high-carbohydrate challenge were found to have a non-normal distribution and were log-transformed for the analyses. Linear regression models were used to assess the racial differences in plasma NP levels. Choosing white race as a reference, a relative percentage difference in plasma NP levels with 95% confidence interval (CI) in blacks was calculated using the following formula: $(e^{\beta} - 1) \times 100$ (where β is the beta coefficient from linear regression). Linear mixed-effect models excluding missing data (<1%) from 72 individuals were used to assess the effect of a high-carbohydrate challenge over time on plasma NP levels. In these models, we assessed for repeated measurements of NP levels with fixed effects of race, time, and their multiplicative interaction term (race*time), accounting for the correlation among repeated measures in the same person. Participants were treated as random effects in these models. The percentage difference with 95% CI in plasma NP levels after 8 hours in overall as well as by race was calculated: $[(e^{\beta} - 1) \times 100 \text{ multiplied by 8 hours (where } \beta \text{ is the beta coefficient from linear regression)}]$. The models mentioned above were further assessed after adjusting for their baseline demographics [i.e., age, sex, body mass index (BMI), insulin].

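### The overall and within-race 8-hour NP change is an uncontrolled change from baseline, so it cannot be attributed to the carbohydrate challenge

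*Combined protocol and SAP*

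**What the plan says.** The Study Protocol section describes one protocol visit, at which everyone receives the same glucose drink. Participants arrive at 7:00 AM after a 10-hour overnight fast, and blood is drawn hourly for 8 hours. Apart from the drink, nothing but distilled water is taken: "All the participants remained in fasting state (except distilled water) till the end of the study protocol". No water-only visit, comparator arm or series of samples before the drink is described.

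The Statistical Analyses section sets the sample size on a within-group change: "Our study was powered to detect the change in ANP levels in response to a high-carbohydrate challenge among black individuals". For a fixed group of 30 black participants it then states: "our study was powered to detect a change as small as 11% in ANP levels after a high-carbohydrate challenge". The mixed models have race, time and their interaction as fixed effects, with participant as a random effect, and they "were used to assess the effect of a high-carbohydrate challenge over time on plasma NP levels". The output is an 8-hour percentage change, overall and for each race. Adjusted versions add age, sex, BMI and insulin, listed as baseline characteristics.

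**The concern.** A time coefficient in a single-condition study measures everything that changes between the first and last sample. The plan gives that coefficient a causal name, the effect of the challenge. It does so for the pooled estimate, for each race separately, and for the quantity that fixed the sample size.

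If the label stays, a fall in NP over the visit will be reported as a response to carbohydrate even where some or all of it would have occurred without the drink. Equally, a flat profile could be read as no response when background change had offset one. Only the race-by-time contrast has any protection, because change common to both races cancels there. The study was not sized on that contrast.

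**Working it through.** **Step 1: what the stated 11% represents.** Inputs from the Statistical Analyses section: n = 30 black participants, SD 0.2, alpha 0.05, and a beta of 0.8 that is evidently meant as power. Two assumptions are needed because the text is silent: SD 0.2 is the SD of the within-person change in log ANP, and the test is two-sided.

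- Standard error = 0.2/√30 = 0.0365.
- Normal approximation: (1.960 + 0.842) × 0.0365 = 0.102.
- Noncentral t on 29 df: 0.106. On the ratio scale this is an 11.2% rise or a 10.0% fall.
- Alternatives fit less well. A one-sided test gives 0.091 to 0.093. Reading beta literally, as 20% power, gives 0.041. A two-group comparison with 30 per group and SD 0.2 gives 0.145.

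The plan's figure is therefore reproduced as a one-sample pre/post calculation. No control enters it.

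**Step 2: what the model can identify.** Write g for the slope in log NP caused by glucose and h for the slope from everything else during the visit, with subscripts W and B for race. With whites as reference:

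- time coefficient = g_W + h_W;
- time + race-by-time (the slope in blacks) = g_B + h_B;
- race-by-time = (g_B − g_W) + (h_B − h_W).

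Everyone receives the drink at time zero, so g and h always appear as a sum in the first two lines. Adding baseline age, sex, BMI and insulin does not help, because a fixed baseline value cannot separate two components of the same time trend. In the third line h drops out only if h_B = h_W.

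**Step 3: what else changes over the 8 hours.** From the Study Protocol section:

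- Time without food, apart from the glucose drink, goes from 10 hours to 10 + 8 = 18 hours.
- The clock goes from a 7:00 AM arrival to about 3 PM or somewhat later, since the time of the drink is not given.

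The documents state neither the size nor the direction of any resulting change in NP.

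**Step 4: illustration under assumed drift.** Take g = 0, keep n = 30, SD 0.2 and a two-sided 5% t-test, and suppose a non-glucose fall over 8 hours. These falls are assumptions, not figures from the documents.

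| Assumed non-glucose fall over 8 h | Log scale | Divided by SE 0.0365 | Chance of a significant result |
|---|---|---|---|
| 3% | 0.030 | 0.83 | 12% |
| 5% | 0.051 | 1.40 | 27% |
| 8% | 0.083 | 2.28 | 60% |
| 11% | 0.117 | 3.19 | 87% |

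The last row corresponds to ln(0.89)/8 = −0.0146 per hour, a compounded fall of about 1.45% per hour. The table uses a two-point paired test, not the planned mixed model.

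**The case against.** The strongest reply is that the study asks about racial differences in response, that the race-by-time term addresses this, and that shared drift cancels there. That stands, and it is why the point is confined to the overall and within-race estimates. It does not remove the point, because the plan reports those estimates as challenge effects and was powered on one of them.

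A second reply is that Step 4 is the plan's own power curve with the word effect replaced by drift. That is correct. The table does not show that drift exists. It shows only that the test responds to a change whatever its cause.

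A third is that diet, fasting and position are standardised. Standardisation makes participants comparable with one another. It does not hold NP constant within a visit.

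Several stronger readings are tempting, and the documents do not support them:

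- **Sodium falls to zero during the follow-up.** The run-in diet averaged 4,667 mg per day, but the overnight fast had already stopped food 10 hours before arrival. Intake therefore does not change between baseline and hour 8.
- **An unbroken 18-hour fast.** The glucose drink interrupts it.
- **A posture artefact.** Participants "were positioned in the sitting position with the back-rest at 45 degrees and legs elevated" on arrival, but the text does not say that this was held for 8 hours. Heart rate, oxygen saturation and three blood pressure readings are described before the drink, and the timing of the baseline blood draw is not given. An unsettled baseline is conjecture.
- **A flawed comparison with the 27% fall in the prior study.** That figure is planning background. No comparison with it is planned, and the documents do not say how that study was controlled.

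**Conclusion.** The point holds for the overall and within-race 8-hour NP changes, including the powered change in black participants. Each is an uncontrolled change from baseline, and the planned model cannot divide it into a glucose part and a remainder. This follows from the design and the model terms alone and needs no assumption about drift.

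The size of any misattribution is unknown. Under the assumptions of Step 4, the chance of a significant result with no glucose effect ranges from 12% at a 3% background fall to 87% at 11%. These are not error rates of this trial.

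A reader might infer that the challenge has no effect on NP, or that the racial comparison is invalid. Neither follows. Lack of attribution is not evidence of no effect. The race-by-time contrast remains interpretable as a difference in glucose response if non-glucose drift is the same in blacks and whites, an assumption the plan does not state.

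**What to change.** In the Statistical Analyses section, both in the power statement and in the description of the mixed models:

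1. Describe the overall and within-race time coefficients as the NP change over the 8 hours after the challenge under the visit conditions, not as the effect of the challenge.
2. Rest the comparative conclusion on race-by-time, and state that reading it as a difference in glucose response assumes equal non-glucose drift in both races.
3. Say as a limitation that no glucose-free visit or arm was included, so the within-race change is not attributed to glucose.

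The cost is wording only, with no extra visit, participant or assay. The price is a weaker within-race claim.

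Two other remedies are not recommended. Adding hourly glucose or insulin to the model would not support a glucose-specific claim: all participants drink the same amount, so with hour fitted as a factor the remaining variation reflects each person's own metabolism. The text also does not confirm that these were assayed hourly. Changing the timing of positioning comes too late, since the text reports the visits and data in the past tense, with 72 individuals analysed.

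### The natriuretic peptide change labelled as being after 8 hours is a fitted hourly slope multiplied by 8, which in general is not the hour-8 versus baseline change, and no linearity check is described

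*Combined protocol and SAP*

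**What the plan says.** All references are to the combined protocol and SAP.

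- Statistical Analyses: NP levels "were found to have a non-normal distribution and were log-transformed for the analyses". The repeated measures are analysed by mixed models with a participant random effect and "fixed effects of race, time, and their multiplicative interaction term (race*time").
- Same section: "The percentage difference with 95% CI in plasma NP levels after 8 hours in overall as well as by race was calculated". The formula takes the hourly percentage (e^β − 1) × 100 from one coefficient, "multiplied by 8 hours".
- Same section, separately: "Linear regression models were used to assess the racial differences in plasma NP levels". The only assumption check described is for normality.
- Study Protocol: one 75 g glucose drink, then "Blood was drawn in 60 min intervals for 8 hours for biomarker profiling" and "All the participants remained in fasting state (except distilled water) till the end of the study protocol".
- The sample-size paragraph gives an expected size but no time course: "a high-carbohydrate challenge can reduce circulating plasma ANP levels up to 27" per cent. It expects a similar effect in whites.

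**The concern.** A reader will take a percentage difference after 8 hours to be the level at hour 8 compared with baseline. What is computed is the best-fitting straight line on the log scale, with its hourly percentage multiplied by 8. The two need not agree.

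The design makes the question a live one. There is a single stimulus at time zero followed by 8 hours without food, and nothing in the documents supports a constant hourly decline over that period. If NP falls and then recovers, a straight line averages the two phases. The same line carries the race comparison: the race-by-time term compares slopes, so two groups whose dips differ in depth can have equal slopes, or slopes that differ in the misleading direction. Since racial difference in the response is the subject of the study's title, both the headline change and the headline comparison depend on the unstated shape.

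**Working it through.** **Inputs from the documents.** Hourly sampling for 8 hours; log NP; the formula 8 × (e^β − 1) × 100; 72 participants in the mixed models; a fall of up to 27%; SD 0.2; 30 black participants; detectable change 11%.

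**Assumptions.** Samples at t = 0, 1, …, 8; piecewise-linear log profiles with a 27% maximum fall, ln(0.73) = −0.3147; 36 participants per race. Every shape and every racial gap below is assumed, because the documents give none.

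**1. The plan's own figure.** For a within-person change with n = 30, SD 0.2, two-sided α 0.05 and 80% power: 0.2 × (1.960 + 0.842)/√30 = 0.102, or +10.8% after back-transformation. The noncentral-t version gives 0.106, or +11.2%. The stated 11% is reproduced. It belongs to a simple change, not to a slope. It also suggests that 0.2 is the SD of a paired change, which gives a residual SD of 0.2/√2 = 0.14. The plan does not say what the 0.2 refers to, so 0.14, 0.2 and 0.3 are used in step 3.

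**2. What the 8-hour formula returns.** With complete data and a random intercept, the fitted slope is b = Σ(t − 4)y / Σ(t − 4)², and Σ(t − 4)² = 60.

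- Fall complete by 1 h and sustained: Σ(t − 4)y = −0.3147 × 4 = −1.259, so b = −0.0210 and 8 × (e^b − 1) = −16.6%.
- Nadir at 2 h, recovered by 6 h: the fractions of the full fall at hours 1 to 5 are 0.5, 1, 0.75, 0.5 and 0.25. Weighted by (t − 4) they sum to −4, so b = −0.3147 × (−4)/60 = +0.0210 and the result is +17.0%.

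| Assumed shape (maximum fall 27%) | b per hour | Plan's figure | True hour-8 change | Geometric mean change, hours 1–8 |
|---|---|---|---|---|
| Log-linear fall | −0.0393 | −30.9% | −27.0% | −16.2% |
| Complete by 1 h, sustained | −0.0210 | −16.6% | −27.0% | −27.0% |
| Nadir 2 h, half recovered by 6 h | −0.0039 | −3.1% | −14.6% | −18.7% |
| Nadir 2 h, recovered by 6 h | +0.0210 | +17.0% | 0.0% | −11.1% |
| Nadir 4 h, recovered by 8 h | 0 | 0.0% | 0.0% | −14.6% |
| Nadir 6 h, recovered by 8 h | −0.0140 | −11.1% | 0.0% | −14.6% |

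The first row is a pure back-transformation error: (e^(8b) − 1) × 100 would return −27.0%. In the fifth row the plan's figure is right for hour 8, but 7 of the 8 post-dose samples lie below baseline and the dip is not visible.

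**3. The race comparison.** Take assumed falls of 27% and 13.5%. The gap in depth on the log scale is ln(0.73) − ln(0.865) = −0.170. For the 2 h/6 h dip the slope difference is −0.170 × (−4)/60 = +0.011 per hour, so the group with the deeper fall shows the larger rise. Power at residual SD 0.14, 0.2 and 0.3 (slope test simulated, with lack of fit in its residual; joint 8-df race-by-time test analytic):

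| Shape | Slope test | Joint test |
|---|---|---|
| Nadir 2 h, recovered by 6 h | 64%, 40%, 22% (virtually all in the misleading direction) | 99%, 78%, 38% |
| Nadir 4 h, recovered by 8 h | 2%, 3%, 4% | 97%, 70%, 33% |
| Log-linear fall | nearly 100%, 94%, 64% | 96%, 68%, 32% |

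**4. Precision.** With residual SD σ, the hour-8 minus baseline contrast has per-person standard error √2 σ, and 8 × slope has 8σ/√60. The ratio is 1.414/1.033 = 1.37.

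**The case against.** The strongest reply is that the harm is wholly conditional. No time course is given, every shape above is assumed, and the largest distortion needs an early dip with full recovery. This stands: it limits what can be said about size, though an unknown shape is also the reason for a model that does not impose one.

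Three stronger readings are tempting, and the documents do not support them.

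- A reader might infer that linearity was never checked. The section is a short retrospective summary. It describes no such check, which is a weaker statement. The linear coding of time is likewise an inference from the formula, though no other coding fits it.
- A reader might infer that the figure is right only when the response is near linear. The symmetric 4 h dip is far from linear and gives the correct hour-8 value; an exactly log-linear fall gives the wrong one.
- A reader might infer that the study's result is wrong, or that a fall was reported as a rise. Nothing in the documents shows which shape occurred.

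Three further replies have some force. The formula is printed, so a careful reader can see that the figure is slope-based, though the label still says otherwise. The separate linear regressions give racial differences in levels, but not in change, so they mitigate only in part. The power statement concerns change within black participants and expects a similar effect in whites, so the two-fold racial gap used above is an illustration and not the plan's own target.

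**Conclusion.** The point holds in a conditional form. The 8-hour percentage is a fitted slope times 8, presented as an 8-hour change, with no hour-specific contrast or linearity check described although hourly samples exist.

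One part needs no assumption about non-linearity: multiplying the hourly percentage by 8 misstates even an exactly log-linear fall, by 3.9 percentage points at a 27% fall. The rest depends on the shape. Under the assumed profiles the discrepancy ranges from none at hour 8, with a hidden dip, to a 17-point rise reported where the true hour-8 change is zero. For a racial gap in dip depth, the slope test has almost no power if the dip is symmetric about 4 h, and it points the misleading way if the dip is early. If the response is truly log-linear, the slope is the more powerful test.

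The change should be made. Confidence is medium, because the actual time course is not in the documents.

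**What to change.** 1. State how time was coded.
2. Fit time as a nine-level factor (0 to 8 h) with race-by-time. In place of slope × 8, report the hour-8 minus baseline contrast as (e^contrast − 1) × 100 with 95% CI, overall and by race, and show the contrasts for the other hours.
3. Report the joint race-by-time test beside the existing slope test. Name one main racial comparison, and do not let a preliminary linearity test choose it.
4. If a slope-based 8-hour figure is kept, label it as such and compute it as (e^(8β) − 1) × 100.
5. The analysis section is in the past tense and reports observed distributions. If the data have already been analysed, label the new analyses post hoc.

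**Cost.** Wording and code only; no new samples. The hour-8 contrast has a standard error about 1.37 times that of slope × 8 under a random intercept. If the response is truly linear, the joint test loses power to the slope test: about 68% against 94% at residual SD 0.2 for the assumed gap of 27% against 13.5%. This is why the slope test stays. The extra tests add multiplicity unless one is named as main.

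### Does the plan need to promise a confidence interval for the race difference in the 8-hour natriuretic peptide change?

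*Combined protocol and SAP*

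**What the plan says.** The title is "Racial Differences in the Natriuretic Peptide Response to Glucose Challenge". There is no separate section for objectives or hypotheses.

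The sample-size paragraph of Statistical Analyses addresses a within-group quantity: "Our study was powered to detect the change in ANP levels in response to a high-carbohydrate challenge among black individuals". Its inputs are "With an estimated standard deviation of 0.2 (a high estimate) and utilizing prespecified sample size of 30 black individuals", with 80% power and α = 0.05, and it arrives at a detectable change of 11%. It expects an effect of similar size in whites.

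The analysis paragraph has three relevant parts:

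- A linear regression comparison of the races: "Choosing white race as a reference, a relative percentage difference in plasma NP levels with 95% confidence interval (CI) in blacks was calculated". This concerns NP levels.
- A mixed model of the repeated log NP values in 72 people, with "fixed effects of race, time, and their multiplicative interaction term (race*time") and participants as random effects.
- The 8-hour summaries: "The percentage difference with 95% CI in plasma NP levels after 8 hours in overall as well as by race was calculated". The percentage per hour is exponentiated first and then "multiplied by 8 hours (where" β is the model coefficient).

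**The concern.** A question about racial differences in response is answered by a difference in change between the races. The plan lists intervals for the pooled change, for each race's change, and for the race difference in levels. None of these is the difference in change.

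Two within-race intervals can mislead if read side by side. Take an assumed example with SD 0.2 on the log scale:

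- Black participants (n = 30) have an 8-hour ratio of 0.94, 95% CI 0.875 to 1.010. This includes no change.
- White participants (n = 42) have a ratio of 0.90, 95% CI 0.847 to 0.956. This excludes it.

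A hasty reader would see a racial difference, but the ratio of the two changes is 0.94/0.90 = 1.04, 95% CI 0.95 to 1.15. The opposite error is to read a non-significant interaction as proof of a similar response. If the report gave only the by-race intervals, or only an interaction p-value, the reader would not see directly how large a racial difference the data still allow.

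**Working it through.** **1. The plan's own figure.** Inputs from the sample-size paragraph: n = 30, SD 0.2, power 0.8, α = 0.05. I take the test as two-sided and the SD as that of the change in log ANP; neither is stated.

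- Normal approximation: 0.2 × (1.960 + 0.842)/√30 = 0.1023 log units; exp(0.1023) − 1 = 10.8%.
- Noncentral t: 0.1058 log units; exp(0.1058) − 1 = 11.2%.

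Both round to 11%. The figure stands, and it refers to the change within black participants. The plan states no power for the race difference, so none is missed.

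**2. What the model yields.** With time linear in hours, as the 8-hour multiplier implies, let b be the race-by-time coefficient per hour on the log scale. The race difference in 8-hour change is 8b, and the ratio of changes is exp(8b). Its limits are exp(8 × each limit of b). The coefficient and its standard error are ordinary output of the model already specified, so no further model or data are needed.

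**3. Can a reader recover the contrast from the by-race results?** Assumed example: a fall of 11% in 30 black participants and 27% in 42 white participants, SD 0.2 in each. The 11% and 27% are the sample-size paragraph's figures, used here only as an example.

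- The printed formula gives p = 800 × [exp(ln(r)/8) − 1]. For r = 0.89, p = −11.57%. For r = 0.73, p = −30.86%.
- The inverse is log change = 8 × ln(1 + p/800). It returns ln(0.89) = −0.1165 and ln(0.73) = −0.3147.
- The same inverse applied to the interval limits recovers the standard errors: 0.2/√30 = 0.0365 and 0.2/√42 = 0.0309.
- The groups contain different people, so the variances add: √(0.0365² + 0.0309²) = 0.0478.
- The difference is −0.1165 + 0.3147 = 0.1982. The ratio is exp(0.1982) = 1.219, with 95% CI exp(0.1982 ± 1.96 × 0.0478) = 1.110 to 1.339.

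The direct contrast, 0.89/0.73 = 1.219 with the same standard error, gives the same interval. A reader who took the printed percentages at face value would get (1 − 0.1157)/(1 − 0.3086) = 1.28. That discrepancy comes from multiplying by 8 after exponentiating, which is a separate matter from whether the contrast is listed.

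**4. How precise would the contrast be?** The documents do not settle this. With 72 people split 30/42 or 36/36 (assumed), SD 0.2 and a two-sample t interval:

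- The standard error is 0.2 × √(1/30 + 1/42) = 0.0478, or 0.2 × √(1/36 + 1/36) = 0.0471.
- The half-width is 1.994 × SE = 0.095 or 0.094 log units. An estimate of no difference would carry a ratio CI of about 0.91 to 1.10.
- The plan says "Blood was drawn in 60 min intervals for 8 hours for biomarker profiling". If there are nine samples and the 0.2 is pure sampling noise, the SD of the fitted 8-hour change is (0.2/√2) × 8/√60 = 0.146. The half-width is then 0.069 to 0.070.

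These values assume that each person has their own slope. The plan names no random slope. If only the intercept is random and the 0.2 is entirely true slope variation, the printed half-width is about 0.033 against a true standard error of 0.048. Coverage is then about 2Φ(0.033/0.048) − 1, roughly 50%. The width of the interval therefore depends on the random-effects structure, which is a different question from whether the interval is listed.

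**The case for a change.** The strongest case for acting is that the fix costs one sentence and one result line, and that the number concerned answers the title. A plan should name the estimate that answers its main question, and by-race intervals are a poor substitute, as the 0.94 and 0.90 example shows. Serial correlation, an unstated random slope and the unusual percentage formula all make reconstruction by a reader less comfortable than a printed contrast.

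Much of this is fair as reporting advice. A report that prints exp(8b) with its limits is easier to read, and a non-significant interaction should be read by its interval. But the advice concerns presentation of a term that is already fitted. The plan nowhere proposes to infer similarity from non-significance; the similar effect expected in whites is a planning assumption. The plan's text is also retrospective and reports that the distributions had been examined. A sentence added now would be a post hoc label and could not make the contrast prespecified. The formula and the random-effects structure may deserve attention in their own right, but they do not turn an unlisted interval into a missing analysis.

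**Conclusion.** No change to the plan follows. The omission is real but is one of detail. The race difference in response is in the model, and its estimate, standard error and test come out of the analysis as described. Competent analysts would report the coefficient with its interval without being told to, and a careful reader could rebuild it from the by-race results (1.219, 1.110 to 1.339 in the example, by either route). No stated sample size, power or detectable effect is affected.

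This rests on time entering linearly in hours and on the unadjusted model, where the two races' slopes are essentially independent apart from shared variance estimates. I attach no weight to a particular precision for the contrast: the race split of the 72 and the scale of the 0.2 are not given, and the half-width runs from about 0.03 to 0.10 log units depending on how person-to-person slope variation is modelled.

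### The 8-hour percentage change multiplies the hourly percentage by 8 instead of compounding it, so falls are overstated and rises understated

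*Combined protocol and SAP*

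**What the plan says.** In the Statistical Analyses section, plasma NP levels "were found to have a non-normal distribution and were log-transformed for the analyses". The back-transformation uses e^β, so the logs are natural. A linear mixed model with race, time and race-by-time terms is then fitted to the repeated measurements. The Study Protocol section gives the sampling: "Blood was drawn in 60 min intervals for 8 hours for biomarker profiling".

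For the effect of the challenge, the section states: "The percentage difference with 95% CI in plasma NP levels after 8 hours in overall as well as by race was calculated". The formula that follows takes (e^β − 1) × 100 and has it "multiplied by 8 hours". No other part of the document gives a different conversion for the 8-hour change.

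Earlier in the same section, the comparison of NP levels between races uses (e^β − 1) × 100 with no time multiplier. That is correct for a contrast of that kind.

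**The concern.** With a natural-log outcome and time in hours, β is the log change per hour. Log changes add over time, but percentage changes do not: they compound. The stated formula converts one hour to a percentage and then adds that percentage eight times. The order should be the reverse: multiply on the log scale, then convert.

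The study's power statement concerns the change in ANP after the challenge, and its title concerns how that response differs by race. The affected formula produces the size of that change for each race. The error grows with the size of the fall, so it does not cancel when the races are compared. It also puts the study's estimates on a different scale from the prior-study reduction that the plan cites.

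**Working it through.** **Inputs from the document (Statistical Analyses, unless noted)**
- Outcome: natural log of NP level.
- Stated 8-hour conversion: 8 × (e^β − 1) × 100.
- Sampling: hourly for 8 hours (Study Protocol section).
- Reference effects: a reduction of up to 27% in a prior study, and a detectable change of 11%.
- SD 0.2, 30 black participants, α 0.05, and 0.8 for power (printed as β).

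**Assumption.** Time enters as a linear term in hours. The factor of 8 implies this, but the plan does not say so.

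**The plan's own figure.** For a paired change with two-sided α (sidedness is not stated), the normal approximation gives a detectable change of 0.2 × (1.960 + 0.842)/√30 = 0.102. The noncentral t calculation gives 0.106, which rounds to the stated 11%. The power statement therefore reproduces, and the conversion does not affect it.

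**Direction of the error.** Write h = e^β − 1 for the hourly proportional change.
- Correct 8-hour change: (1 + h)^8 − 1 = e^(8β) − 1.
- Stated 8-hour change: 8h.

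By Bernoulli's inequality (1 + h)^8 > 1 + 8h for every h > −1 other than 0. The stated value is therefore always the lower of the two, which overstates falls and understates rises.

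**Size.** For a true 8-hour proportional change c, β = ln(1 + c)/8. For c = −0.27, β = ln(0.73)/8 = −0.03934 and e^β − 1 = −0.03858. The stated formula gives 8 × (−3.858%) = −30.9%. In the same way:

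| True 8-hour change | Stated formula | Error (points) |
|---|---|---|
| −11% | −11.6% | −0.6 |
| −27% | −30.9% | −3.9 |
| −40% | −49.5% | −9.5 |
| −50% | −66.4% | −16.4 |
| −70% | −111.8% | −41.8 |
| +11% | +10.5% | −0.5 |
| +50% | +41.6% | −8.4 |

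Only the 11% and 27% magnitudes come from the plan. The other rows show how the error grows.

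**Impossible values.** The stated formula reaches −100% at h = −12.5%, that is β = ln(0.875) = −0.1335 per hour. The correct 8-hour change there is 0.875^8 − 1 = −65.6%.

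**Confidence limits (illustration).** Assume the 8-hour log change has SE 0.2/√30 = 0.0365. Around a true −27%, the log-scale limits are −0.3147 ± 1.96 × 0.0365, or −0.3863 and −0.2431.
- Correct: e^(−0.3863) − 1 = −32.0% and e^(−0.2431) − 1 = −21.6%, a width of 10.5 points.
- Stated: 8 × (e^(−0.3863/8) − 1) = −37.7% and 8 × (e^(−0.2431/8) − 1) = −23.9%, a width of 13.8 points.

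**Comparison between races (hypothetical).** If one race truly fell by 27% and the other by 13.5%, the stated formula would give 30.9% and 14.4%. The gap would grow from 13.5 to 16.5 points.

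**The case against.** The strongest reply accepts the algebra and disputes how much it matters.

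- **Inference does not change.** The sign of each estimate, the test of β = 0, the race-by-time test and whether an interval excludes zero all stay the same. This is correct, and it confines the error to the size of the effect and the position and width of its interval.
- **The error is modest at the plan's own figures.** It is 0.6 points at 11% and 3.9 points at 27%. The 27% is an upper figure from a prior study in whites, with no 8-hour horizon given. This also stands. Even so, 3.9 points is about one-seventh of a 27% effect.
- **The larger cases are hypothetical.** The plan expects a similar effect in whites, so the 27% against 13.5% comparison is only an illustration. A fall beyond 65.6% is more than twice the largest reduction cited. A value below −100% therefore shows that the formula is invalid and does not predict a result.
- **The code may already use e^(8β).** The document contains no results or code, so this cannot be excluded. If so, only the wording is wrong, but anyone following the text would still get wrong numbers.
- **The plan names no primary endpoint.** That the 8-hour change is central is inferred from the power statement and the title.

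None of these points makes the stated formula right.

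**Conclusion.** The concern holds: the formula is wrong as written. For any nonzero slope it gives an 8-hour percentage change below the true one, and it shifts both confidence limits the same way. At the effect sizes in the plan, a fall is overstated by 0.6 points (11%) to 3.9 points (27%), and the error rises quickly for steeper slopes. Hypothesis tests, the power statement and the race comparison that has no time multiplier are unaffected.

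The sizes rest on natural logs, which e^β implies, and on time being linear in hours. If time were categorical, multiplying by 8 would have no meaning and the text would still need correction. Whether any figure has in fact been miscalculated cannot be told from the document.

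**What to change.** 1. State how time is coded in the mixed model.
2. For linear time in hours, replace the formula with (e^(8β) − 1) × 100, where β is the overall or race-specific slope. The race-specific slope combines the time and race-by-time coefficients.
3. Obtain the 95% CI by multiplying each limit of that slope by 8 and applying the same transformation.
4. If time is categorical, use (e^d − 1) × 100, where d is the model contrast of hour 8 minus hour 0, and transform the limits of d in the same way.
5. Check the code, and recalculate any 8-hour percentages and intervals that came from the stated formula.

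The cost is one line of wording and code plus the recalculation. No new data are needed and no test result changes. Any falls calculated with the stated formula will become smaller, and any rises larger.
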